10.6.4 Additional Secondary Efficacy

Additional secondary efficacy analyses will repeat those in the preceding sections (confirmatory primary and secondary efficacy analyses), when using PP analysis population instead of ITT (**Error! Reference source not found.**, **Error! Reference source not found.**).

Analysis of additional secondary efficacy endpoints (defined in Section 6.2.3) will be conducted on both ITT and PP analysis populations.

Descriptive statistics of raw values and change or percent change from baseline, as appropriate, over time by treatment group will be provided for the following:

- Clinical Rating Scale for Tremor (CRST) Parameters:
 - Part A and B CRST, separately for treated and non-treated side of the body (**Error! Reference source not found.**, **Error! Reference source not found.**)
 - Part B Score for treated side of the body, for each motor task (**Error! Reference source not found.** – **Error! Reference source not found.**)
 - Part C Score for each item and Overall (**Error! Reference source not found.** – **Error! Reference source not found.**)
 - Overall CRST Score (**Error! Reference source not found.**)
- Quality of Life in Essential Tremor Questionnaire (QUEST) Parameters:
 - Overall Quality of Life Score (**Error! Reference source not found.**)

- Waking Hours with Tremor in Any Body Part (**Error! Reference source not found.**)
- Tremor Severity Score, separately for each category (**Error! Reference source not found. – Error! Reference source not found.**)
- QUEST Parameters (based on questions 1-30):
 - Dimension Score, separately for each dimension (**Error! Reference source not found. – Error! Reference source not found.**)
 - Summary of Dimensions Total Score (**Error! Reference source not found.**)

In addition, where appropriate, the following will be provided:

- Graphical presentation over time by treatment group
- Statistical testing to compare:
 - between treatment groups, by visit
 - within each treatment group, comparing Baseline to each follow-up visit
 - between treated and non-treated sides, within each treatment group, by visit

10.6.5 Covariate Analyses

The effects of covariates will be assessed for all confirmatory primary and secondary efficacy analyses.

The following covariates will be examined:

- Age
- Baseline CRST Score (CRST_[contralateral, Baseline])
- Gender
- Center

Center is expected to have several categories. Keeping the number of categories as is will, in some cases, yield small subgroups and substantially reduce power. To address this issue, categories will be combined by grouping those with few observations into a

single category. Grouping of categories will be specified after category frequency have been produced but before statistical testing.

The following will be provided:

1. Analyses for PE, SE1 and SE3 will be conducted on ITT analysis population comparing ExAblate and Sham groups. The following model will be applied:

$$Y = \text{Covariate} + \text{Treatment Group} + \text{Covariate} * \text{Treatment Group}$$

Where,

Y = PE, SE1 or SE3, depending on the analysis

Covariate = covariate of interest

*Covariate*Treatment Group* = covariate by group interaction

Models both with and without *Covariate*Treatment Group* interaction will be considered (**Error! Reference source not found.**).

Statistical testing will be done by linear regression. In case the distribution of Y is extremely not normal, the non-parametric methods will be applied depending on the emerged distribution.

Descriptive statistics of each endpoint will be presented by covariate levels and treatment group. For this purpose numerical covariates (Age and Baseline CRST Score) will be categorized into equal subgroups inside the emerged range of values (**Error! Reference source not found.**, **Error! Reference source not found.**, **Error! Reference source not found.**).

Assessing the effect of a covariate on treatment will be done by examining the degree to which the significance of the Treatment Effect changes with the inclusion of the covariate (**Error! Reference source not found.**). Weakening or strengthening of the Treatment Effect in the presence of a covariate will be interpreted using both clinical and statistical considerations.

2. Analyses for SE2 will be conducted on the ITT (subjects from ExAblate group only) population and will repeat the second confirmatory secondary efficacy analysis for each level of covariate separately. For this purpose numeric covariates (Age and Baseline CRST Score) will be categorized into equal subgroups inside the emerged range of values.

Descriptive statistics of SE2 will be presented by covariate levels (**Error! Reference source not found.**). In addition, for numeric covariates a scatter

plot of SE2 versus covariate will be produced (**Error! Reference source not found., Error! Reference source not found.**). If no trend is observed, as shown on mock figures, the conclusion would be that the covariate has no effect on SE2.

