4.1.5 Videotaping Procedure

The CRST assessments will be videotaped at all visits Baseline through Month 12; Routine Screening CRST video assessments may be obtained and used by core lab as a quality assurance check for videotaping techniques to provide feedback on best taping practices. Screening CRST assessments will not be used in determination of pivotal study endpoints. The goal of the videotaping procedure is to ensure a uniform format to enable the Core Lab assessor to score all subjects utilizing the same filming procedure. This procedure is NOT meant to train assessors how to perform tremor assessment. The CRST assessment will be done by qualified movement disorder specialists.

The videotaping protocol is provided in **Appendix B**. The videotaping protocol should be followed by all sites to provide a standardized format for core lab scoring as well as site scoring utilizing the same sequences. The videotaping protocol provides a suggested sequence grouped by position to minimize discomfort of the subject and relocation of the camera. Additionally, the items are grouped by body region and task for each position.

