Physical Exam	X			X	X	X	X	X	X
Neurological Status	X		X	X	X	X	X	X	X
CRST (Unblinded Site Assessor)	X							X	X
CRST (Blinded Site Assessor)		X				X	X		
CRST (Blinded Tremor Core Lab)		X				X	X	X	X
QUEST	X	X				X	X	X	X
PHQ-9	X					X	X	X	X
CT		X							
MRI		X							X
Treatment			X						
Adverse Events			X	X	X	X	X	X	X
Exit Form									X

5 Analysis Populations

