4. Denote the treated (contralateral) upper extremity CRST sub score at visit [k] as CRST_[contralateral, k], then:

$$\text{CRST}_{[\text{contralateral, k}]} = \frac{\text{Part A} + \text{Part B}}{\text{Total}}$$

Where, *Total* is the maximal sum that could be achieved in Part A and Part B, based on the available items (obtained and imputed). Note that Total should be re-adjusted for each patient based on his/her available information.

For example, if the following conditions for a subject hold

- The treated side of the body is ipsilateral to handedness,
- One item in Part A is missing
- All five items in Part B are obtained

then the Total = 8 (Maximum that could be achieved in Part A) + 20 (Maximum that could be achieved in Part B) = 28

Note: Lower CRST_[contralateral, k] scores are better than higher scores.

5. The confirmatory primary efficacy endpoint (denoted as PE) – Percent Improvement from Baseline at three months post-treatment in the treated (contralateral) upper extremity CRST sub score – will be calculated as follows:

$$PE = \frac{CRST_{[contralateral, Baseline]} - CRST_{[contralateral, 3\ months\ FU]}}{CRST_{[contralateral, Baseline]}} \times 100$$

Note: higher PE values represent improvement.

For both stages (Main and Crossover) the primary efficacy endpoint will be calculated using Baseline score, measured before Main stage treatment initiation.

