6.2.2 Confirmatory Secondary Endpoints

The confirmatory secondary efficacy endpoints in this study are the following:

- SE1=Improvement from Baseline at three months in Quality of Life in Essential Tremor (QUEST). SE1 will be calculated as follows:
 - Categorize the 30 questions into 5 dimensions as follows:
 - Communication: #1 – #3
 - Work and Finances: #4 – #9
 - Hobbies and Leisure: #10 – #12
 - Physical: #13 – #21
 - Psychosocial: #22 – #30
 - Score all applicable questionnaire answers as follows:
 - Never = 0
 - Rarely = 1
 - Sometimes = 2
 - Frequently = 3
 - Always = 4

Note:

- ✓ All questions answered “N/A” will be excluded from the calculation (only questions 4, 5, 7, 8 and 14 can be answered “N/A”)

- ✓ Questions 6, 7, 11 and 12 can only be scored at two values – either a 0 or a 4
- For each subject, calculate dimension score as a percentage of total possible score for each dimension separately. Denote dimension score for dimension [i] at visit [k] as $DS_{[i,k]}$, then:

$$DS_{[i,k]} = \frac{\text{Total applicable points}_{[i,k]}}{\text{Total possible points} (\# \text{ of applicable questions} \times 4)_{[i,k]}} \times 100$$

Note: missing data should be imputed as described in Section 7.2.1.

- For each subject, calculate QUEST summary of dimensions total score as a mean of the five dimension scores. Denote QUEST summary of dimensions total score at visit [k] as $QUEST_{[k]}$, then:

$$QUEST_{[k]} = \frac{\sum_{i=1}^5 DS_{[i,k]}}{5}$$

Note: lower QUEST_[k] scores are better than higher scores.

- For each subject, calculate SE1 as follows:

$$SE1 = \frac{QUEST_{[\text{Baseline}]} - QUEST_{[3 \text{ months FU}]}}{QUEST_{[\text{Baseline}]}}$$

Note: higher SE1 values represent improvement.

- SE2=Percent Improvement from Baseline at twelve months post-treatment in the treated (contralateral) upper extremity CRST sub score. SE2 will be calculated similarly to PE from the previous section, based on 12 months FU data.
- SE3=Percent Improvement from Baseline at three months post-treatment in functional disabilities CRST total score, as measured by CRST Part C. Note, that Part C is performed by Site Assessor only. SE3 will be calculated for each subject as follows:
 - Denote functional disabilities CRST Part C total score at visit [k] as $CRST_C_{[k]}$, then:

CRST_C_[k] = average of answers to items #16-#23 at visit [k]

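### The severity covariate in SAP 10.6.5 is the denominator of PE and SE2, so rating error in Baseline creates a false severity gradient in both and a smaller false interaction for PE

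*SAP*

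**What the plan says.** SAP 6.2.1 defines the primary endpoint PE as "Percent Improvement from Baseline at three months post-treatment in the treated (contralateral) upper extremity CRST sub score", that is, 100 x (Baseline - Month 3)/Baseline, with "CRST_{[contralateral, Baseline" in the denominator. For SE2, SAP 6.2.2 states: "SE2 will be calculated similarly to PE from the previous section, based on 12 months FU data".

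SAP 10.6.5 then lists "Baseline CRST Score (CRST_[contralateral, Baseline" among four covariates and uses it in two ways:

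- **Regression.** The outcome is "Y = PE, SE1 or SE3, depending on the analysis". Each is regressed on treatment and the covariate, with and without their interaction, and also summarised by covariate level.
- **SE2, ExAblate arm only.** The one-sample test is repeated within covariate categories. For numeric covariates a "plot of SE2 versus covariate will be produced", and the absence of a visible trend is taken to mean no covariate effect.

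Neither document mentions the shared term or the reliability of a CRST reading. The SAP 4 schedule also has a CRST at Screening, in the row "CRST (Unblinded Site Assessor". Of that reading, Protocol 4.1.5 (Videotaping Procedure) says: "Screening CRST assessments will not be used in determination of pivotal study endpoints".

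**The concern.** An observer-rated tremor score carries some rating error. When the observed Baseline is both the divisor of the endpoint and the covariate, its error enters both sides of the comparison with the same sign. PE and SE2 then rise with Baseline even if true percent benefit has nothing to do with severity.

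In the PE model the gradient scales with what remains after treatment, so it is steeper in Sham. The ExAblate-Sham difference therefore seems to shrink with severity, while improvement within each arm seems to grow. A reader of the PE model, the tables by Baseline level or the SE2 plot could conclude that benefit depends on severity when it does not. Protocol 5.6 says the covariate analyses are there to judge how generally the results apply.

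SE1 and SE3 have their own denominators (QUEST and CRST Part C), so they are not coupled to this covariate by construction.

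**Working it through.** SAP 10.6.5 gives no figure to reproduce, so the check derives the slope and then simulates the planned model.

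**Inputs from the documents**
- Protocol 5.4: pilot mean 20.4 falling to 4.7, stated as 78% (1 - 4.7/20.4 = 77.0%, close), versus 4% untreated. The protocol labels this Total CRST; taking 20.4 as the level of the sub score is an assumption.
- Long-term follow-up protocol, section 18 (used only for calibration): PE 46.9% (95% CI 40.3 to 53.5, N=56) versus -0.1% (-9.6 to 9.5, N=20); Month 12, 39.6%. The ExAblate half-width is (53.5 - 40.3)/2 = 6.6. Dividing by t = 2.00 and multiplying by √56 gives a PE SD of about 24.6.

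**Inputs that are assumed:** observed Baseline SD 5; reliability r of one reading 0.9, 0.8 or 0.7.

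**Slope.** Let true severity be T with mean μ, Baseline B = T + error, and follow-up F = T(1 - d) + independent error, with the same proportional benefit d for everyone in an arm. Since E[T|B] = rB + (1 - r)μ,

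E[PE|B] = 100{1 - (1 - d)[r + (1 - r)μ/B]},

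and the slope at B = μ is 100(1 - d)(1 - r)/μ. It is zero only if r = 1. For example, for Sham at r = 0.8: 100 x 1 x 0.2/20.4 = 0.98.

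| PE points per Baseline point, μ = 20.4 | r = 0.9 | r = 0.8 | r = 0.7 |
|---|---|---|---|
| Sham, d = 0 | 0.49 | 0.98 | 1.47 |
| ExAblate Month 3, d = 0.469 | 0.26 | 0.52 | 0.78 |
| ExAblate Month 12 (SE2), d = 0.396 | 0.30 | 0.59 | 0.89 |

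A fitted straight line is steeper than this local value, because the curve is steeper at low Baseline. The mean simulated slopes at r = 0.8 were 1.22 (Sham) and 0.67 (ExAblate). In the same setting the apparent ExAblate-Sham difference was 50.6 points in the lowest Baseline tertile and 45.0 in the highest, with no true difference.

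**Rejection rates.** 56 ExAblate and 20 Sham, nominal level 5%, true benefit varying between patients with SD 20 points and unrelated to severity. At r = 0.8 this gives an ExAblate PE SD of about 25, near the 24.6 above.

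| Planned PE model | error-free Baseline | r = 0.9 | r = 0.8 | r = 0.7 |
|---|---|---|---|---|
| Baseline term, 46.9% vs 0 | 5% | 14% | 30% | 47% |
| Interaction, 46.9% vs 0 | 6% | 9% | 12% | 14% |
| Interaction, 78% vs 4% | 4-6% | 10% | 17% | 20% |

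Further runs with r between 0.66 and 0.75, and benefit varying by the same SD, gave 41-57% for the baseline term and 7-13% for the interaction. If benefit is identical for all patients, interaction rates are higher, but about 10% of trials then reject even with an error-free Baseline because the arm variances differ. Those rates therefore cannot all be put down to rating error.

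**SE2.** The SAP plans no slope test. As a gauge of how visible the trend would be, an ExAblate-only slope test at 46.9% benefit was significant in about 9/18/31% of trials at r = 0.9/0.8/0.7.

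**The case against.** The strongest reply is that these analyses are supportive and the damage is limited. Much of that stands.

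- The covariate analyses lie outside the testing hierarchy of SAP 10.6.1. The stated reading rule for PE is how far the significance of treatment changes when the covariate is added. Treatment stayed significant in every simulated trial, so that rule would not overturn the primary result.
- Protocol 5.6 already urges care in interpretation, though on grounds of chance findings and not this artefact. Raw sub scores by arm and visit will also be reported.
- Reliability and Baseline SD are assumed, so the size is uncertain even though the direction is not.
- Screening differs from Baseline in rater, timing and medication-stability status.

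Three stronger readings are tempting but unsupported. A reader might infer that SE2 is also regressed on Baseline and shows a false interaction; SAP 10.6.5 limits the regression to "Y = PE, SE1 or SE3, depending on the analysis", and the SE2 analysis has no control arm. A reader might infer that a false PE interaction is likely; at the 46.9% effect it is only modestly above nominal. A reader might infer that the primary comparison is biased; randomisation balances Baseline error between arms, so it is not.

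What the reply does not remove is the false baseline slope. Nothing in 10.6.5 would let an analyst recognise it, and the SE2 plot rule would not identify a false trend as an artefact.

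**Conclusion.** The point holds for a supportive analysis and should be corrected before the covariate analyses are run. Any rating error in Baseline gives PE a positive baseline slope in both arms, steeper in Sham, and gives SE2 a false upward trend. Under the stated assumptions the false baseline term is the main problem (about 14/30/47% against 5%). The false interaction is smaller: about 9/12/14% at 46.9% versus 0, and 10/17/20% at the planning effect.

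The direction follows from the definitions alone. The size rests on an assumed Baseline SD of 5, reliability of 0.7 to 0.9, a mean of 20.4 and benefit varying by SD 20 points. No confirmatory conclusion changes.

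**What to change.** In SAP 10.6.5, for PE and SE2 only:

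1. Use the same-limb sub score from the Screening CRST as the severity covariate in the PE models, and as the axis for the Baseline-severity subgroups, tables and SE2 scatter plot.
2. Fit the PE interaction model with robust standard errors.
3. State that a trend against the Baseline sub score will not be read as effect modification.

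The Screening reading precedes randomisation and does not enter PE. Using it as a covariate is compatible with Protocol 4.1.5, since it determines no endpoint. In simulation, with Screening error independent of Baseline error, this returned the PE interaction and the ExAblate-only slope to about 4-7%. Robust errors alone, with Baseline kept as covariate, did not fully cure the problem: the interaction still rejected in up to 12% of trials at the planning effect.

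The cost is a short SAP edit and one changed input variable, with no new data and no change to a confirmatory test. The price is a noisier severity measure, scored by an unblinded site assessor instead of the Core Lab and before the medication-stability visit. The documents do not allow that loss to be quantified.

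A model of log Month 3 score on log Baseline, treatment and their interaction is acceptable only as a supplement. It needs a pre-stated rule for zero scores, which are plausible given a pilot post-treatment mean of 4.7.

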10.6.3 Confirmatory Secondary Efficacy

As indicated in Section 6.2.2, this study has three confirmatory secondary endpoints (SE1, SE2 and SE3). Hierarchical testing design will be applied to control for multiple statistical testing (as explained in Section 10.6.1).

SE1 Analysis:

The first confirmatory secondary efficacy analysis will be conducted on the ITT analysis population. The following hypothesis will be tested for SE1:

$$H_0: Q3_{\text{ExAblate}} \leq Q3_{\text{Sham}}$$

$$H_1: Q3_{\text{ExAblate}} > Q3_{\text{Sham}}$$

Where, $Q3_{\text{ExAblate}}$ and $Q3_{\text{Sham}}$ are means of the first Secondary Endpoint (SE1), as defined in Section 6.2.2, in the ExAblate and Sham groups, respectively.

This hypothesis will be analyzed using independent groups t-test with two-sided alpha=0.05, should the data not differ appreciably from normal theory. Otherwise, the Wilcoxon rank-sum test will be applied. Descriptive statistics and comparison p-value will be provided (**Error! Reference source not found.**).

SE2 Analysis:

The second confirmatory secondary efficacy analysis will be conducted on the ITT (subjects from ExAblate group only) population. The following hypothesis will be tested for SE2:

$$H_0: M12_{\text{ExAblate}} \leq 0$$

$$H_1: M12_{\text{ExAblate}} > 0$$

Where, $M12_{\text{ExAblate}}$ is the mean of the second Secondary Endpoint (SE2), as defined in Section 6.2.2, in the ExAblate group.

This hypothesis will be analyzed using one-sample t-test with two-sided Alpha = 0.05, should the data not differ appreciably from normal theory. Otherwise, the one-sample Wilcoxon signed rank test will be applied. Descriptive statistics and comparison p-value will be provided (**Error! Reference source not found.**).

SE3 Analysis:

The third confirmatory secondary efficacy analysis will be conducted on the ITT analysis population. The following hypothesis will be tested for SE3:

$$H_0: C3_{\text{ExAblate}} \leq C3_{\text{Sham}}$$

$$H_1: C3_{\text{ExAblate}} > C3_{\text{Sham}}$$

Where, $C3_{\text{ExAblate}}$ and $C3_{\text{Sham}}$ are means of the third Secondary Endpoint (SE3), as defined in Section 6.2.2, in the ExAblate and Sham groups, respectively.

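### For SE2, the SAP turns the absence of an observed trend into a finding of no covariate effect, and its level-by-level tests against zero cannot show whether levels differ

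*SAP*

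**What the plan says.** SE2 is the percent improvement from baseline to Month 12 in the treated upper extremity CRST score (SAP 6.2.2). SAP 10.6.3 defines the population: "The second confirmatory secondary efficacy analysis will be conducted on the ITT (subjects from ExAblate group only) population". The test compares the mean with zero: "This hypothesis will be analyzed using one-sample t-test with two-sided Alpha = 0.05, should the data not differ appreciably from normal theory". A signed rank test is the fallback.

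SAP 10.6.5 then lists four covariates: age, baseline CRST score, gender and center. For SE2 it plans the following.

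- The covariate analysis "will repeat the second confirmatory secondary efficacy analysis for each level of covariate separately".
- To form levels, "numeric covariates (Age and Baseline CRST Score) will be categorized into equal subgroups inside the emerged range of values". The number of subgroups is not given.
- "Descriptive statistics of SE2 will be presented by covariate levels".
- For age and baseline CRST there is also a scatter plot, with this reading rule: "If no trend is observed, as shown on mock figures, the conclusion would be that the covariate has no effect on SE2".

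No slope, correlation, confidence interval or comparison between levels is planned for SE2. For PE, SE1 and SE3 the same section fits the covariate with treatment, with and without their interaction: "Statistical testing will be done by linear regression".

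**The concern.** There are two separate faults.

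First, failing to see a trend is lack of evidence, and the SAP commits to reporting it as evidence of absence. Nothing in the rule reflects how precisely about 50 subjects can estimate a trend.

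Second, the formal tests do not address the covariate question. A test of each level's mean against zero asks whether that subgroup improved. Two levels can both pass while differing a great deal, and two levels with the same true mean can split into one significant and one not because one is small.

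What is at stake is the statement about generalisability. Protocol 5.6 gives that as the purpose of the covariate work and urges caution in reading it. SE2 is the confirmatory durability endpoint, so a reader could be told that durability does not depend on age or baseline severity when the data have not shown this. The long-term follow-up protocol (ET002-LTF, section 15.7) adopts the pivotal SAP's procedures. The rule could therefore be reused there, although that section does not mention covariates.

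**Working it through.** The documents give no power or precision for the SE2 covariate analysis, so there is no stated figure to reproduce.

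**Inputs**

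- Planned ExAblate n: 60 evaluable subjects at 3:1 (Protocol 5.4) gives 60 × 3/4 = 45.
- Reported ExAblate n: 56, with Month 12 mean improvement 39.6% and 95% CI 34.0% to 45.3% on the composite tremor/motor score (ET002-LTF, section 18, efficacy table). These are results, not planning values, and only set a realistic scale.
- SD, back-calculated: half-width (45.3 − 34.0)/2 = 5.65; SD = 5.65 / t(0.975; 55 df) × √56 = 5.65/2.004 × 7.483 = 21.1 points.
- Assumptions: bins of 19 (three bins) or 14 (four bins), because the SAP gives no number; and SD 21.1 within each bin.

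**1. What a flat plot can exclude**

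The Fisher z interval around an observed correlation of 0 is ± tanh(1.96/√(n − 3)).

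- n = 45: tanh(1.96/√42) = tanh(0.302) = 0.29
- n = 56: tanh(1.96/√53) = tanh(0.269) = 0.26

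In SE2 units, per 1 SD of the covariate, this is 0.294 × 21.1 = 6.2 points or 0.263 × 21.1 = 5.5 points, in either direction.

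Power for a true correlation r is approximately P(Z > 1.96 − atanh(r) × √(n − 3)).

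| True r | n = 45 | n = 56 |
|---|---|---|
| 0.2 | 26% | 31% |
| 0.3 | 52% | 62% |
| 0.4 | 78% | 87% |

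**2. Level-wise tests when levels truly differ**

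Take two bins with true means 29.6 and 49.6, a difference of 20 points. The one-sample noncentrality is mean/SD × √n.

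| Per bin | Low bin rejects zero | High bin rejects zero | Direct test of the 20-point difference |
|---|---|---|---|
| 19 | 29.6/21.1 × √19 = 6.1; above 0.999 | above 0.999 | 20/(21.1 × √(2/19)) = 2.9; 0.81 |
| 14 | 29.6/21.1 × √14 = 5.2; 0.998 | above 0.999 | 20/(21.1 × √(2/14)) = 2.5; 0.68 |

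If both bins have mean 39.6, each also rejects zero with probability of about 1. The planned tests therefore give the same result whether the difference is 20 points or none.

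**3. Level-wise tests when levels do not differ but one is small**

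At a true mean of 39.6, a bin of 3, 4 or 5 subjects rejects zero with probability 0.43, 0.71 or 0.87. Under the signed rank fallback, the smallest exact two-sided p-value with 5 subjects is 2 × (1/2)^5 = 0.0625, so such a bin could never reach 0.05. Significance can thus differ between levels through size alone.

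**4. Baseline CRST as a covariate**

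SE2 is (baseline − Month 12)/baseline × 100 (SAP 6.2.1 and 6.2.2), so measurement error in baseline enters both axes of the plot. An illustrative simulation had no true dependence and 56 subjects. It assumed baseline mean 0.6 and SD 0.12 on the 0 to 1 score, and follow-up at 0.6 of the true score with noise SD 0.1. The mean correlation was 0.27, 0.14 and 0.08 at assumed baseline reliabilities of 0.6, 0.8 and 0.9. Neither a trend nor its absence can be taken at face value for this covariate.

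**The case against.** The strongest reply is that little depends on this. The analysis is supportive; the SE2 test, the testing hierarchy in SAP 10.6.1 and the primary endpoint are untouched, and PE, SE1 and SE3 already get regression. Readers will also have SE2 by covariate level with mean, SD, range and n (SAP 10), plus full data listings (SAP 11), so differences between levels and bin sizes will be visible. All of this stands and limits the weight of the point. It does not rescue the rule: the descriptive tables carry no interval for a difference, and the SAP's stated conclusion is still no effect.

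Three stronger readings are tempting, and the documents do not support them.

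- A reader might infer equal-width bins with sparse ends. The text says only that the variables "will be categorized into equal subgroups inside the emerged range of values"; equal width and equal counts both fit. The defensible statement is that the binning is unspecified.
- A reader might infer that nearly every bin will be significant whatever the covariate does. That fails for small bins (step 3), and for a covariate strong enough to bring a bin's mean near zero.
- A reader might infer that the plot is judged purely by eye. That is likely, since no criterion is written, but the mock figures are not available here and might carry a fitted line. The inference from no trend to no effect is invalid either way.

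**Conclusion.** The rule is wrong as written, and of minor consequence. For age and baseline CRST, the SAP draws a conclusion of no effect that the analysis cannot support. A perfectly flat result leaves true correlations of up to 0.29 (n = 45) or 0.26 (n = 56) open, roughly 6 points of SE2 per SD of the covariate. For all four covariates, the only formal SE2 tests cannot tell levels that differ from levels that do not.

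The correlation limits depend only on n. The figures in points and for bins rest on the reported mean of 39.6, the back-calculated SD of 21.1 and assumed bin sizes. The logical fault depends on none of these. A reader might infer that the confirmatory SE2 result or the type I error rate is compromised. It is not, because the covariate analysis stands outside the hierarchical tests; only the generalisability statement is affected.

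**What to change.** Rewrite the SE2 item of SAP 10.6.5, for the ExAblate ITT group, as follows.

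- Age and baseline CRST: regress SE2 on the continuous covariate and report the slope with its 95% CI beside the scatter plot.
- Gender and center (after the planned grouping): report between-level differences in mean SE2 with 95% CIs.
- Replace the no-effect conclusion with no evidence of a trend, to be read with the interval.
- Keep the subgroups and level-wise results as descriptive only, without tests against zero, and state the number of subgroups and whether equal means width or count.
- For baseline CRST, either state that the slope is coupled to the outcome through the divisor, or model the Month 12 score on the baseline score instead.

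The cost is one rewritten item, its mock tables and figures, and a few lines of analysis code. No new data, visits or subjects are needed, and the confirmatory tests stay as they are.
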